## **7.0 TRIAL PROCEDURES**

### **7.1 Trial Procedures**

The Trial Flow Chart - Section 6.0 summarizes the trial procedures to be performed during each cycle. Individual trial procedures are described in detail below. It may be necessary to perform these procedures at unscheduled time points if deemed clinically necessary by the investigator.

Furthermore, additional evaluations/testing may be deemed necessary by the PI and/or Merck for reasons related to subject safety. In some cases, such evaluation/testing may be potentially sensitive in nature (e.g., HIV, Hepatitis C, etc.), and thus local regulations may require that additional informed consent be obtained from the subject. In these cases, such evaluations/testing will be performed in accordance with those regulations.

#### **7.1.1 Administrative Procedures**

##### **7.1.1.1 Informed Consent**

The Investigator must obtain documented consent from each potential subject prior to participating in a clinical trial.

###### **7.1.1.1.1 General Informed Consent**

Consent must be documented by the subject's dated signature or by the subject's legally authorized representative's dated signature on a consent form along with the dated signature of the person conducting the consent discussion.

A copy of the signed and dated consent form should be given to the subject before participation in the trial.

The initial informed consent form, any subsequent revised written informed consent form and any written information provided to the subject must receive the IRB's approval/favorable opinion in advance of use. The subject or his/her legally authorized representative should be informed in a timely manner if new information becomes available that may be relevant to the subject's willingness to continue participation in the trial. The communication of this information will be provided and documented via a revised consent form or addendum to the original consent form that captures the subject's dated signature or by the subject's legally acceptable representative's dated signature.

The informed consent will adhere to IRB requirements, applicable laws and regulations and Sponsor-Investigator requirements.

9458- Protocol Version Date 28 Feb 2019

### **7.1.1.2 Inclusion/Exclusion Criteria**

Prior to enrollment, all inclusion and exclusion criteria will be reviewed by the investigator or qualified designee to ensure that the subject qualifies for the trial.

### **7.1.1.3 Medical History**

A medical history will be obtained by the investigator or qualified designee. Medical history will include all active conditions, and any condition diagnosed within the prior 10 years that are considered to be clinically significant by the Investigator. Details regarding the disease for which the subject has enrolled in this study will be recorded separately and not listed as medical history.

### **7.1.1.4 Prior and Concomitant Medications Review**

#### **7.1.1.4.1 Prior Medications**

The investigator or qualified designee will review prior medication use, including any protocol-specified washout requirement, and record prior medication taken by the subject within 28 days before starting the trial. Treatment for the disease for which the subject has enrolled in this study will be recorded separately and not listed as a prior medication.

#### **7.1.1.4.2 Concomitant Medications**

The investigator or qualified designee will record medication, if any, taken by the subject during the trial. All medications related to reportable SAEs and ECIs should be recorded as defined in Section 7.2.

### **7.1.1.5 Disease Details and Treatments**

#### **7.1.1.5.1 Disease Details**

The investigator or qualified designee will obtain prior and current details regarding disease status.

#### **7.1.1.5.2 Prior Treatment Details**

The investigator or qualified designee will review all prior cancer treatments including systemic treatments, radiation and surgeries.

#### **7.1.1.5.3 Subsequent Anti-Cancer Therapy Status**

Once new anti-cancer therapy has been initiated the subject will move into survival follow-up.

### **7.1.1.6 Assignment of Enrollment Number**

Once a subject has enrolled, they will be assigned a unique identifying number for the purposes of tracking and collecting data.

9458- Protocol Version Date 28 Feb 2019

### **7.1.1.7 Trial Compliance (Medication/Diet/Activity/Other)**

The investigator or qualified designee will review compliance with study requirements at study visits and as deemed necessary.

## **7.1.2 Clinical Procedures/Assessments**

### **7.1.2.1 Adverse Event (AE) Monitoring**

The investigator or qualified designee will assess each subject to evaluate for potential new or worsening AEs as specified in the Trial Flow Chart and more frequently if clinically indicated. Adverse experiences will be graded and recorded throughout the study and during the follow-up period according to the most current available version of the NCI CTCAE (see Section 12.2). Toxicities will be characterized in terms regarding seriousness, causality, toxicity grading, and action taken with regard to trial treatment.

Please refer to section 7.2 for detailed information regarding the assessment and recording of AEs.

### **7.1.2.2 Full Physical Exam**

The investigator or qualified designee will perform a complete physical exam during the screening period (and at time points indicated in the Trial Flow Chart). Clinically significant abnormal findings should be recorded as medical history.

### **7.1.2.3 Directed Physical Exam**

For cycles that do not require a full physical exam per the Trial Flow Chart, the investigator or qualified designee will perform a directed physical exam as clinically indicated prior to trial treatment administration.

### **7.1.2.4 Vital Signs**

The investigator or qualified designee will take vital signs at screening, prior to the administration of each dose of trial treatment and at treatment discontinuation as specified in the Trial Flow Chart (Section 6.0). Vital signs should include temperature, pulse, respiratory rate, weight and blood pressure.

### **7.1.2.5 Eastern Cooperative Oncology Group (ECOG) Performance Scale**

The investigator or qualified designee will assess ECOG status (see Section 12.1) at screening, prior to the administration of each dose of trial treatment and discontinuation of trial treatment as specified in the Trial Flow Chart.

### **7.1.2.6 Assessment of Disease**

Bone marrow examinations will be the primary modality for disease assessments on this study. The bone marrow performed for screening/eligibility may be performed at an outside

9458- Protocol Version Date 28 Feb 2019

institution, provided an assessment of morphology was performed that confirmed morphologic CR and MRD was detected by either MFC or PCR. If the marrow exam was performed > 28 days before the start of treatment or if either of these elements is not available, a repeat bone marrow exam will be required prior to enrollment.

Following the initiation of treatment, bone marrow exams will be repeated after each of the first 2 cycles of treatment. These should be performed  $3 \pm 1$  days prior to the start of the subsequent cycle (i.e., Day 18-20) to provide adequate time for interpretation. At a minimum, bone marrow exams will include an evaluation of morphology as well as a repeat analysis of whatever study (or studies) detected MRD at the time of enrollment (e.g., if MRD was detected by MFC and PCR at enrollment, follow-up marrow exams should include both MFC and PCR); other studies may be included as clinically indicated.

If morphologic relapse (i.e., leukemic blasts in the peripheral blood or  $\geq 5\%$  blasts in the bone marrow not attributable to any other cause) is detected at any time, treatment will stop and the subject will be removed from the study. However, subjects with persistent MRD may continue, provided other criteria to continue study treatment are met.

As our institution's standard methods for MRD detection in ALL are either MFC or PCR for the *BCR-ABL* fusion product in patients that have Ph+ disease, it is anticipated that these will be the primary modalities by which MRD is monitored. That said, for patients from whom adequate baseline material is available, NGS performed in the UW Hematopathology Laboratory or at Adaptive Biotechnologies will be used as an additional method of MRD monitoring. These results, however, will not be available in real time, and thus clinical decision-making will rest entirely on the results of MFC and/or PCR.

For subjects who are eligible to proceed to Cycles 3 and beyond, bone marrow exams will be repeated after every other cycle (i.e., Cycle 4, 6, and 8) through Cycle 8. For those eligible to continue beyond Cycle 8, the timing of subsequent bone marrow exams will be left to the treating investigator, though every 3 months while receiving study treatment will be recommended.

A bone marrow exam will also be required at the end of treatment. If the decision to discontinue treatment coincides with the timing of one of the above follow-up assessments, a separate end-of-treatment examination will not be required (e.g., the post-cycle 4 bone marrow demonstrated morphologic relapse). Similarly, if morphologic relapse is detected after Cycle 1, no further bone marrow examinations will be required for this study.

For definitions of response categories, please see Section 12.3.

Imaging studies will only be performed if extramedullary disease is suspected based on the evaluation of the treating investigator. This may occur at screening (to ensure eligibility) or at end of treatment (to document relapse/progression). If extramedullary disease is identified, this will constitute disease relapse: study treatment will be discontinued, and the subject will be removed from the study.

9458- Protocol Version Date 28 Feb 2019

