#### **5.1.2 Subject Inclusion Criteria**

In order to be eligible for participation in this trial, the subject must:

1. Be willing and able to provide written informed consent for the trial.
2. Be  $\geq 18$  years of age on day of signing informed consent.
3. Presence of MRD (defined as  $< 5\%$  blasts in the bone marrow by morphologic assessment and no clinically-apparent extramedullary disease but with quantifiably-measurable disease as assessed by either MFC or PCR) under any of the following circumstances:
  - a. MRD persistence  $\geq 11$  weeks after the start of initial therapy,
  - b. MRD persistence  $\geq 2$  weeks after the start of salvage therapy, or
  - c. MRD reappearance at any time.

9458- Protocol Version Date 28 Feb 2019

4. For patients with Ph+ disease, have previously received treatment with  $\geq 1$  ABL kinase inhibitor (e.g., imatinib, dasatinib, etc.) or are ineligible for such treatment.
5. Have previously received or are ineligible for treatment with blinatumomab. Ineligibility will include (but not be limited to) CD19-negative disease, denial of insurance coverage, physician discretion, and/or patient refusal.
6. Be willing to provide tissue from a newly obtained bone marrow aspirate and/or biopsy. Newly-obtained is defined as a specimen obtained up 28 days prior to initiation of treatment on Day 1. Subjects for whom newly-obtained samples cannot be provided (e.g., inaccessible or subject safety concern) may submit an archived specimen only upon agreement from the PI.
7. Have a performance status of 0 to 1 on the ECOG Performance Scale.
8. Demonstrate adequate organ function as defined in Table 1, all screening labs should be performed within 10 days of treatment initiation.

Table 1: Adequate Organ Function Laboratory Values

System	Laboratory Value
Hematological	
Absolute neutrophil count (ANC)	$\geq 1,000$ /mCL
Hemoglobin	$\geq 8$ g/dL
Platelets	$\geq 50,000$ / mCL
Renal	
Serum creatinine OR Measured or calculated a creatinine clearance (GFR can also be used in place of creatinine or CrCl)	$\leq 1.5$ X upper limit of normal (ULN) OR $\geq 60$ mL/min/1.73 m  for subject with creatinine levels $> 1.5$ X institutional ULN
Hepatic	
Serum total bilirubin	$\leq 1.5$ X ULN OR Direct bilirubin $\leq$ ULN for subjects with total bilirubin levels $> 1.5$ ULN
AST (SGOT) and ALT (SGPT)	$\leq 2.5$ X ULN
Coagulation	

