### 5.1.3 Subject Exclusion Criteria

The subject must be excluded from participating in the trial if the subject:

1. Is currently participating and receiving study therapy or has participated in a study of an investigational new drug and received study therapy or used an investigational device within 4 weeks of the first dose of treatment.
2. Has a diagnosis of immunodeficiency or is receiving systemic steroid therapy or any other form of immunosuppressive therapy within 7 days prior to the first dose of trial treatment.
3. Has a known history of active TB (Bacillus Tuberculosis).
4. Has a known hypersensitivity to pembrolizumab or any of its excipients.
5. Has had a prior anti-cancer monoclonal antibody (mAb) within 4 weeks prior to study Day 1 or who has not recovered (i.e.,  $\leq$  Grade 1 or at baseline) from adverse events due to agents administered more than 4 weeks earlier.
6. Has had prior chemotherapy, targeted small molecule therapy, or radiation therapy within 2 weeks prior to study Day 1 or who has not recovered (i.e.,  $\leq$  Grade 1 or at baseline) from adverse events due to a previously administered agent.
  - Note: Subjects with  $\leq$  Grade 2 neuropathy or with hematologic toxicity that has recovered to levels above that stated in Inclusion Criterion 6 are an exception to this criterion and may qualify for the study if all other inclusion/exclusion criteria are met.
  - Note: If subject received major surgery, they must have recovered adequately from the toxicity and/or complications from the intervention (i.e.,  $\leq$  Grade 1 or at baseline) prior to starting therapy.
7. Has a known additional malignancy that is progressing or requires active treatment. Exceptions include basal cell carcinoma of the skin or squamous cell carcinoma of the skin that has undergone potentially curative therapy or in situ cervical cancer.
8. Has known active central nervous system (CNS) leukemia and/or leukemic meningitis. Subjects with previously treated CNS leukemia may participate provided they are stable (e.g., without evidence of active disease by imaging for at least four weeks prior to the first

9458- Protocol Version Date 28 Feb 2019

dose of trial treatment and any neurologic symptoms have returned to baseline) and have no evidence of leukemic blasts on analysis of cerebrospinal fluid (CSF).

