### **5.5.2 Prohibited Concomitant Medications**

Subjects are prohibited from receiving the following therapies during the Screening and Treatment Phase (including retreatment for post-complete response relapse) of this trial:

- Antineoplastic systemic chemotherapy or biological therapy
- Immunotherapy not specified in this protocol
- Chemotherapy not specified in this protocol
- Investigational agents other than pembrolizumab
- Radiation therapy
- Live vaccines within 30 days prior to the first dose of trial treatment and while participating in the trial. Examples of live vaccines include, but are not limited to, the following: measles, mumps, rubella, varicella/zoster, yellow fever, rabies, BCG, and typhoid vaccine.
- Systemic glucocorticoids for any purpose other than to modulate symptoms from an event of clinical interest of suspected immunologic etiology. The use of physiologic doses of corticosteroids may be approved after consultation with the PI.

Subjects who enroll in the context of persistent MRD following prior treatment will not be allowed to continue this prior treatment. Subjects who, in the assessment by the investigator, require the use of any of the aforementioned treatments for clinical management should be

9458- Protocol Version Date 28 Feb 2019

removed from the trial. Subjects may receive other medications that the investigator deems to be medically necessary.

The Exclusion Criteria describes other medications which are prohibited in this trial.

There are no prohibited therapies during the Post-Treatment Follow-up Phase.

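### The baseline MRD-positive marrow may precede up to about 14 days of prior anti-leukemic therapy, and clearance from that therapy would count as a pembrolizumab response

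*Combined protocol and SAP*

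**What the plan says.** **Age and source of the marrow.** Section 5.1.2, criterion 6: "Newly-obtained is defined as a specimen obtained up 28 days prior to initiation of treatment on Day 1". Section 7.1.2.6: "The bone marrow performed for screening/eligibility may be performed at an outside" institution, and a repeat before enrollment is needed only "If the marrow exam was performed > 28 days before the start of treatment" or if the morphology or MRD result is missing.

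**Washouts (Section 5.1.3).** Exclusion 6: "Has had prior chemotherapy, targeted small molecule therapy, or radiation therapy within 2 weeks prior to study Day 1". Exclusion 5: "Has had a prior anti-cancer monoclonal antibody (mAb) within 4 weeks prior to study Day 1". Exclusion 1 applies the same 4 weeks to investigational agents. Exclusions 11 and 12 date MRD detection from a transplant or cell infusion (at least 21 days after it). No equivalent exists for drug therapy or radiation.

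**Qualifying MRD.** Section 5.1.2, criterion 3b, admits MRD persistence at least 2 "weeks after the start of salvage therapy, or" on reappearance at any time under 3c. Criterion 3b counts from the start of salvage, not from its end.

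**Therapy during screening.** Section 5.5.2: "Subjects are prohibited from receiving the following therapies during the Screening and Treatment Phase", followed by a list that includes antineoplastic therapy. Section 6.1 gives screening a window of Day −28 to −1.

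**Endpoint.** Section 12.3 (cited in Section 9.2 as 11.3) defines complete MRD response as MRD negativity, with no carry-over condition. Section 9.2 sets the decision rule: 12 then 21 evaluable subjects, stop to reconsider at 0 of 12, success at 3 or more of 21, against a 5% historical rate with standard chemotherapy.

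**The concern.** The primary endpoint is conversion from a positive baseline marrow to a negative later one, in a single arm. It can be credited to pembrolizumab only if little else happened between the two samples. As written, a subject could have a positive marrow while salvage is still running, receive further doses, complete the 14-day washout and start treatment without a new marrow. The first repeat comes on Day 18–20 of Cycle 1. If the last salvage doses cleared the disease, that marrow would be negative and the subject would be scored a responder.

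Three responses decide the trial, so even one misattributed response carries weight.

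**Working it through.** **1. Length of the gap.** Maximum marrow age minus minimum washout:
- chemotherapy, targeted small molecules, radiation: 28 − 14 = 14 days
- monoclonal antibodies and investigational agents: 28 − 28 = 0 days, so essentially closed
- systemic steroids: exclusion 2 bars a subject who "is receiving systemic steroid therapy or any other form of immunosuppressive therapy within 7 days prior to the first dose of trial treatment", so 28 − 7 = 21 days. The documents do not say whether steroids inside a leukemia regimen fall under this rule or under exclusion 6, so the point rests on the 14-day figure.

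**2. Do other provisions close it?**
- Section 5.5.2 also stops subjects enrolled with persistent MRD from continuing their prior treatment. If screening begins at consent, neither rule reaches doses given between an outside marrow and consent.
- Section 12.3 defines persistence by at least two quantifiable time points with a treatment element between, so a single reading does not satisfy 3b. But the second reading need not follow the last dose.
- Exclusion 14 lets the investigator exclude for therapy that might confound the results. It is discretionary and names no interval.

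The gap is narrowed, not closed.

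**3. Reproducing the design.** With b(x) the Bin(12, p) probability:

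P(success) = b(1)·P(Bin(9,p) ≥ 2) + b(2)·P(Bin(9,p) ≥ 1) + P(Bin(12,p) ≥ 3)

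- p = 0.05: 0.3413×0.0712 + 0.0988×0.3698 + 0.0196 = 0.080 (plan: .08)
- p = 0.20: 0.2062×0.5638 + 0.2835×0.8658 + 0.4417 = 0.803 (plan: 80%)
- P(0 of 12) at 20%: 0.8^12 = 0.069 (plan: 0.07)
- Expected size at 5%: 12 + 9×(1 − 0.95^12) = 12 + 9×0.4596 = 16.1 (plan: 16.1)

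The plan's figures are correct.

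**4. One carry-over responder placed at random among 21, the other 20 at 5%.**
- In stage 1 (probability 12/21): at least 2 of the other 20 are needed, 0.264.
- In stage 2 (probability 9/21): stage 1 must still give at least one response: 0.3413×0.3366 + 0.1184 = 0.233.
- Combined: (12/21)×0.264 + (9/21)×0.233 = 0.251.

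**5. Higher background clearance.** The documents do not give the share with intervening therapy or its clearance rate. Assume a 20% share, with everyone else at 5% and no pembrolizumab effect:

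| Clearance in the 20% (assumed) | Background | P(declare success) |
|---|---|---|
| 5%, as in Section 9.2 | 0.80×0.05 + 0.20×0.05 = 5% | 0.080 |
| 5% extra carry-over: 1 − 0.95×0.95 = 9.75% | 0.80×0.05 + 0.20×0.0975 = 5.95% | 0.12 |
| 20% | 0.80×0.05 + 0.20×0.20 = 8% | 0.22 |
| 30% | 0.80×0.05 + 0.20×0.30 = 10% | 0.34 |

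**The case against.** The strongest reply is that the 5% null is a clearance rate under standard chemotherapy, so it already includes conversions caused by chemotherapy. A reader might infer that the null covers none of these conversions. Section 9.2 does not support that. If subjects with intervening therapy clear at 5%, the type I error stays at 0.080. What survives is narrower: the 5% comes from a chemorefractory MRD study, whereas this trial also admits subjects 2 weeks into salvage or at MRD reappearance. Their clearance rate need not be 5%, but no document says that it is higher.

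A reader might also infer that Section 5.5.2 contradicts the 2-week washout. It need not. The 28-day screening window is a maximum, so a screening-phase bar and a 14-day minimum can both be met, and the washout governs when screening is short. What is unclear is when screening begins relative to an outside marrow.

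Finally, scoring flagged responders as failures may discard genuine responses. A subject still MRD-positive on an on-treatment marrow who clears later is poorly explained by carry-over. That is fair, and the fix allows for it.

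**Conclusion.** The gap stands: up to about 14 days of chemotherapy, targeted small-molecule therapy or radiation may fall between the baseline marrow and the washout, and the response definition would credit any resulting clearance to pembrolizumab. It is clearest for therapy given between an outside marrow and consent.

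Its effect on the trial's error rate is not known. The 0.251 is conditional on one carry-over response having occurred. The 0.12 to 0.34 range rests on an assumed 20% overlap and assumed clearance rates. A reader might conclude that the type I error has tripled or quadrupled; the documents give neither the frequency of overlap nor any excess clearance, so they do not support that. They do show that a rule of 3 in 21 is sensitive to a single misattributed response, which justifies a low-cost safeguard on the primary result.

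**What to change.** 1. Reconcile Sections 5.1.2 (criteria 3 and 6), 5.1.3 (exclusion 6), 5.5.2, 6.1 and 7.1.2.6, so that they state how the baseline MRD sample relates in time to the last prior anti-leukemic dose, and when the screening phase begins for a subject with an outside marrow. Which timing rule applies is for the investigators to decide.
2. In Section 9.2, record for each subject the interval from baseline marrow to last prior dose, and flag those with therapy in between.
3. Report the primary result as planned, and again with responses in flagged subjects counted as non-response. List separately any flagged subject who was still MRD-positive on an on-treatment marrow before clearing.

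Sample size and decision rule stay as they are. The cost is some data review: Sections 7.1.1.4.1 and 7.1.1.5.2 provide for recording and reviewing prior treatment but do not mention dates, so these may have to come from the medical records. The sensitivity result may be conservative. Enrollment was estimated to end on 10/1/2018 and this version is dated 28 Feb 2019, so item 1 may affect few subjects; items 2 and 3 remain useful after accrual.
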